3.7. Safety evaluation

Frequencies of side effects will be summarized descriptively per treatment arm and in total. Patient listings will be given.

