Tumor specimens are minced and kept in RPMI medium 1640 under sterile conditions for a maximum of 72 hours. During that time, specimens are shipped to the Medical University of Vienna together with other specimens. Thereafter the tumor pieces are mixed with ultra-pure collagenase III in medium 199 and allowed to incubate at 37°C for 3-4 hours. After incubation, cells are filtered through a 46µl nylon mesh and washed with RPMI/20% FSB, then washed twice with HBSS. Cell are counted and transferred to a 5 ml tube, washed with HBSS and HICS and incubated with Sandoglobin solution for 10 min. After another washing step with HBSS and HICS, antibodies are added. The antibodies are the same as for blood specimen.

Stopping rules (End of Study)

1. Withdrawal of informed consent
2. Death
3. Lost to Follow Up

Risks and Benefits for the patients

Risk of biopsy

Core needle biopsies are routinely performed to preoperatively diagnose breast cancer. Morbidities are bleeding or infections which usually may be treated conservatively. Cell seeding has been demonstrated but the clinical impact is only minor²⁹.

Risk of blood withdraw

Usually there are no complications with venous blood withdraw, however, a thrombophlebitis or local pain and red skin may result from this invasive diagnostic procedure. The risk is between 1 and 5%. Local cooling packs and sometimes antibiotics and bandages may be necessary to reduce the pain and the infection.

Risks of local treatment

The main risk for the patient is for women in the treatment group A (local therapy) who undergo operation under general anesthesia. In general the local treatment (surgical removal of the primary tumor) has been done throughout more than 100 years in metastasized and non-metastasized patients with excellent results. Recently El-Tamer et al published morbidity and mortality rates of mastectomy and lumpectomy in 3107 patients³⁰.

30-day mortality was 0 – 0.24% and 30-day morbidity was between 1.8 and 5.7% showing higher numbers for mastectomized patients. The highest morbidity rate was due to superficial wound infections with 3% in the mastectomy group. Wound infection was associated with adipositas (BMI >30). Sever events such as cardiac arrest or pulmonalembolia were seen in 0.06% or 0.24%, respectively. Thrombophlebitis and systemic infections have been seen in 0.07 – 0.24% and 0.07 - 0.3%, respectively. Acute renal insufficiency has been observed in 0.06% of patients undergoing mastectomy.

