2.2.3. Safety objectives

The safety objective for this study is to evaluate the safety of surgical therapy and local therapy versus no surgery (surgery on demand) and local therapy.

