3.3. Definition of populations for analyses

3.3.1. Intention-to-Treat (ITT) population

Primary and secondary analyses will be based on the Intention-to-Treat (ITT) population; that is, all patients who were included in the randomization. All subjects will be analyzed according to the therapy arm to which they have been randomized. Subjects who terminate the study before their scheduled final study visits will be censored.

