4.5. Safety evaluation

16. Side Effects by SOC in total and by treatment arm

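### The safety objective is met only by crude side-effect frequencies by arm, with no time window and no 30-day post-operative summary, so the comparison is biased if survival differs

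*SAP*

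**What the plan says.** SAP 2.2.3 sets a safety objective: "to evaluate the safety of surgical therapy and local therapy versus no surgery (surgery on demand"), with local therapy named on both sides of the comparison. The analysis for it is two sentences in SAP 3.7: "Frequencies of side effects will be summarized descriptively per treatment arm and in total", and "Patient listings will be given". The table list in SAP 4.5 holds one item, "Side Effects by SOC in total and by treatment arm".

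Neither document defines a side effect, states over what period side effects are collected, or names a safety population. SAP 3.3 defines an ITT and a QoL population and rules out a per-protocol analysis. Under ITT, "All subjects will be analyzed according to the therapy arm to which they have been randomized", but that section is introduced for primary and secondary analyses.

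The protocol section on risks of local treatment names the operation in arm A as the main risk. It describes that risk over 30 days, citing a published surgical series: "30-day mortality was 0 – 0.24% and 30-day morbidity was between 1.8 and 5.7" percent, higher after mastectomy.

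Other planned output touches on safety. SAP 3.4.1 tabulates patients operated and causes of death by arm. SAP 3.4.2 summarises and lists local therapy in arm B as a protocol deviation. SAP 3.4.4 describes exposure to local and systemic treatment. None of these is stated to be timed from surgery or linked to side effects.

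**The concern.** A crude frequency counts whatever happens while a patient is alive and observed. In a survival trial that time differs between arms as soon as survival does, so the safety comparison inherits the primary result. Both arms also receive systemic therapy by centre policy, so a by-arm SOC table mixes a small number of operative complications with drug toxicity.

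Two things are at stake. The trial could report more side effects with surgery when surgery adds none, or conceal a real excess if arm A survives less well. And the risk the protocol presents to justify the operation, complications and death within 30 days, would have no prespecified counterpart in the results.

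**Working it through.** **Inputs.** Median survival 24 months (control) and 36 months (surgery), hazard ratio (HR) 0.666, 127 patients per arm: protocol, sample size considerations. Follow-up visits to month 60: protocol Appendix 4. Literature 30-day morbidity 1.8–5.7% and mortality 0–0.24%: protocol, risks of local treatment. Assumptions not in the documents: exponential survival, no loss to follow-up, collection of side effects throughout follow-up, and a constant side-effect hazard h equal in both arms.

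**The plan's own figure.** The safety section states none. The survival assumptions can be checked on the event count: 4 × (1.960 + 0.842)² / (ln 0.666)² = 190.0, or 191 after rounding up to a whole even split. With HR 2/3 and an assumed inflation of 1.008 for one interim look it is 192.5. The stated 192 events are reproduced.

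**Time at risk to month 60.** λ = ln 2 / median, so λ_A = 0.01925 and λ_B = 0.02888 per month. Mean time at risk = (1 − e^(−60λ)) / λ:
- Arm A: (1 − 0.3150) / 0.01925 = 35.6 months
- Arm B: (1 − 0.1768) / 0.02888 = 28.5 months
- Ratio 1.25

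With uniform 4-year accrual and follow-up to year 9 instead, the means are 41.3 and 31.3 months, ratio 1.32.

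**Crude frequency with no true difference.** The share with at least one side effect before death or month T is h / (h + λ) × (1 − e^(−(h + λ)T)). At T = 60:

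| h per month (assumed) | Arm A | Arm B | Spurious difference |
|---|---|---|---|
| 0.001 | 3.5% | 2.8% | 0.7 points |
| 0.002 | 6.8% | 5.5% | 1.3 points |
| 0.01 | 28.3% | 23.2% | 5.0 points |
| 0.02 | 46.1% | 38.7% | 7.4 points |
| 0.05 | 71.1% | 62.8% | 8.2 points |
| 0.5 | 96.3% | 94.5% | 1.8 points |

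**Direction.** At HR 1 the time-at-risk ratio is 1.00 and the artefact vanishes. At HR 1.5 (arm A median 24 / 1.5 = 16 months) the ratio is 0.75 to month 60 and 0.71 to year 9, so arm A toxicity would be understated.

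**Size of the surgical signal.** 127 × 1.8% = 2.3 and 127 × 5.7% = 7.2 patients with 30-day morbidity; 127 × 0.24% = 0.3 deaths.

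**Effect of a common window.** At T = 6 months, h = 0.01, 0.02 and 0.05 give 5.50 vs 5.35%, 10.69 vs 10.40% and 24.55 vs 23.90%: differences of 0.15, 0.29 and 0.65 points. Over 30 days from randomisation the time-at-risk ratio is 1.005.

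**Why not divide everything by patient-years.** To month 60, 127 patients contribute 127 × 35.6 / 12 = 377 patient-years in A and 127 × 28.5 / 12 = 302 in B. Ten identical early events in each arm become 2.7 and 3.3 per 100 patient-years, a spurious advantage of about 20% for surgery.

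**The case against.** Several stronger statements are tempting, and the documents do not support them.

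- A reader might infer that the plan will charge longer survival to surgery as toxicity. That needs arm A to live longer and side effects to be collected throughout; the first is the trial's question and the second is not stated.
- A reader might infer that the trial cannot measure 30-day risk. Listings, causes of death, operations performed and arm B local therapy are all to be reported. If the listings carry dates, a 30-day count is possible. It is just not prespecified.
- A reader might infer that booking complications of on-demand surgery to arm B is an error. The objective itself defines the comparator as including surgery on demand, so a by-arm table answers it. Analysis as randomised is also an inference for safety: SAP 3.7 says only treatment arm.
- A reader might infer that no patient is seen in the first 30 days because Appendix 4 starts at month 3. Blood is drawn 1–3 days after surgery in arm A at pre-selected centres, and a visit schedule does not define side-effect reporting.

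The objection on size also has force. The hazards are assumed, Table 16 is by SOC, and within a rare SOC the artefact is about 1 point, below the literature morbidity. The 30-day rates are background, not an endpoint. What remains is that the only prespecified comparison is sensitive to survival, and that the named risk has no planned summary.

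**Conclusion.** The point holds in this limited form: the prespecified safety comparison has no window and no account of time at risk, and nothing is timed from the operation. Under the design medians, and if side effects are collected throughout, arm A is at risk 25% longer to month 60. The resulting artefact is 5 to 8 points for common side effects (assumed 0.01 to 0.05 per month) and about 1 point for rare ones. For common side effects that is comparable to, or larger than, the 1.8–5.7% surgical morbidity quoted. It is zero at equal survival and changes sign if arm A fares worse. It does not touch the primary analysis. The 30-day gap does not depend on these assumptions.

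**What to change.** In SAP 3.7 and the table list:

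1. State what counts as a side effect and over what period it is collected.
2. Add a descriptive table of deaths and complications within 30 days of the first breast or axillary operation. Its denominator is patients actually operated, shown separately for planned arm A and on-demand arm B surgery, with exact confidence intervals. It supplements the by-arm table and does not replace it.
3. Give the by-arm side-effect table for one common fixed window from randomisation, for example the first 6 months.
4. Summarise later side effects by cumulative incidence with death as a competing event, not by dividing all events by patient-years. This handles unequal censoring and shows timing, but its late values still depend on survival (without censoring it equals the crude share computed above), so show it beside the death curve.

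The cost is one or two extra tables. Precision will be low: 7 of 127 gives an exact 95% interval of 2.2–11.0%, and 2 of 127 gives 0.2–5.6%. On-demand operations are likely to be very few. All of it depends on side-effect dates having been recorded.

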For the secondary endpoint growth factors, circulating tumor cells, stem cells, post intervention measurements are compared with baseline values and tested with the *repeated measures ANOVA*. Correlations between initial or late drop of growth factors, circulating tumor cells, stem cells and median survival or TTP, respectively, will be calculated with the *Spearman rank order correlation test*. The stem cell and growth factors in the tumor will be correlated with the stem cell and growth factor release into the peripheral circulation and known prognostic factors such as her2neu expression and grading as well as survival time. The association with her2neu expression and grading and categorical variables will be assessed by an *ANOVA*. The association with the survival time will be analysed with a *Cox regression*.

Surgical Therapy

Local therapy consists of lumpectomy or mastectomy with a resection free margin of at least 1 mm or more demonstrated on paraffin embedded histological sections. Intraoperative frozen sections are allowed but not definitive for margin assessment. For axillary surgery, either axillary dissection level I and II or sentinel node biopsy has to be performed (mandatory) which has only to be followed by axillary dissection in case of macrometastasis of at least one sentinel lymph node.

Surgery on demand

In the arm B (no local therapy) it may be necessary to perform local therapy on demand (surgery, radiotherapy). Reasons may be uncontrolled bleeding or infected exulcerations with a septic component and no treatment benefit from conservative therapy. This will be considered as protocol deviation. However, the patient's follow up is recorded and data are available for retrospective analyses as intention to treat.

Radiation therapy

Local radiation therapy of the breast may be given according to center policy in therapy arm A. In arm B this will be considered as protocol deviation. Radiation therapy of the metastases is allowed according to center policy in both arms.

Systemic therapy

Chemotherapy or anti-hormone therapy is used according to center policy. The following recommendations should be followed:

1. In cases of radiotherapy and chemotherapy (arm A), radiotherapy should not be given later than 6 months after surgery. Radiotherapy is allowed in parallel to anti-hormonal treatment.

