Bleedings as well as seroma productions are rare and may be observed in 1 to 2% of patients. Most bleedings and hematoma formations may be treated conservatively while only a minority may need to undergo a second operation.

There is, however, a small risk to need a second operation due to positive resection margins. This risk is reduced by the use of intraoperativen frozen section analyses to 6% ([name] et al; data submitted).

Benefit for the patients

The benefit for the patient may be a 10% absolute increase in median survival from 24 to 36 months. More over if the hypothesis is true that the resection of the primary tumor in metastasized patients increases overall survival, the knowledge about carcinogenesis increases substantially. If we are able to demonstrate that circulating tumor cells and/or growth factors released from the primary tumor may be at least in part responsible for this improvement, the doors are open to investigate new therapeutic strategies in these patients such as anti-growth factor antibodies or systemic therapies destroying tumor stem cells. No trial has been published so far answering these important questions which may, in fact, guide us to new aspects of cancer therapy.

ADMINISTRATIVE REQUIREMENTS

Good Clinical Practice

- The study will be conducted in accordance with the International Conference on Harmonisation (ICH) for Good Clinical Practice (GCP) and the appropriate regulatory requirement(s). Essential clinical documents will be maintained to demonstrate the validity of the study and the integrity of the data collected.

Ethical Considerations

- The study will be conducted in accordance with ethical principles founded in the Declaration of Helsinki (see Appendix 5). The IEC will review all appropriate study documentation in order to safeguard the rights, safety and well-being of the patients.

Patient Information and Informed Consent

The principal investigators at each center will ensure that the patient is given full and adequate oral and written information about the nature, purpose, possible risk and benefit of the study. Patients must also be notified that they are free to discontinue from the study at any time. The patient should be given the opportunity to ask questions and allowed time to consider the information provided.

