3.4.2. Protocol deviations

Important protocol deviations were defined with respect of violations of against the inclusion/exclusion criteria, stratification errors and all deviations from protocol of the study, eg. Local therapy, surgery and/or radiotherapy in arm B or surgery of metastases in both arms.

Summaries of IPDs will be presented per treatment arm and in total. Additionally, patient listings will be given.

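### The safety objective compares surgery with no surgery, but its only measure is an undefined count of side effects that need not capture harm from the tumour left in place in arm B

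*SAP*

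**What the plan says.** SAP 2.2.3 states the safety objective as a comparison: to "evaluate the safety of surgical therapy and local therapy versus no surgery (surgery on demand) and local therapy". SAP 3.7 meets it with "Frequencies of side effects will be summarized descriptively per treatment arm and in total", plus patient listings. The only safety entry in the list of outputs (SAP 4.5, Table 16) is "Side Effects by SOC in total and by treatment arm". Neither document defines side effect or adverse event, sets a causality rule or a collection period, or names a safety population. SAP 3.3 defines an ITT and a QoL population and drops the per-protocol one.

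The Protocol's risk section covers biopsy, blood sampling and local treatment. For surgery it gives 30-day morbidity of 1.8% to 5.7% and adds "Bleedings as well as seroma productions are rare and may be observed in 1 to 2% of patients". It has no entry for the risk of leaving the primary in place.

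That risk appears elsewhere. Under surgery on demand in arm B, the Protocol says: "Reasons may be uncontrolled bleeding or infected exulcerations with a septic component and no treatment benefit from conservative therapy". It then classes the on-demand treatment as a protocol deviation. SAP 3.4.2 follows, giving as examples of important deviations "Local therapy, surgery and/or radiotherapy in arm B or surgery of metastases in both arms", summarised in Table 17 with listings.

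**The concern.** In this trial one arm's local harm comes from operating and the other's from not operating. A measure tied to treatment fits the first better than the second. The same kind of clinical event, a serious bleed or infection at the breast, is clearly reportable when it follows the operation. It is reportable only at the site's discretion when it comes from an untreated tumour.

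At stake is whether the safety table can answer SAP 2.2.3 at all. If tumour complications in arm B are left out, the table shows the local cost of surgery without the local cost of withholding it, and the error runs in one direction, against surgery.

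**Working it through.** The plan states no arm B complication rate and no expected safety difference, so there is no plan figure to reproduce. The check is to follow each event through the planned outputs and then see what a missed event does to the comparison.

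**Where each event goes**

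| Event | Table 16 (side effects) | Table 17 (deviations) |
|---|---|---|
| Arm A, postoperative bleed or wound infection | Yes, on any reading | No |
| Arm B, tumour bleed or sepsis leading to on-demand therapy | Only if the site calls it a side effect | The therapy, not the event |
| Arm B, tumour complication settled conservatively | Only if the site calls it a side effect | No, as no local therapy was given |
| Arm B, complication of on-demand surgery | Can be counted | The therapy, not the event |

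The third row follows from the Protocol's own trigger, which includes failure of conservative treatment. A complication that responds to it causes no deviation and may appear in neither table.

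**Whether another output fills the gap**

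- Time to local progression uses growth of more than 25% or local recurrence (Protocol, secondary endpoints; SAP 3.6.1), not bleeding, infection or ulceration.
- The QLQ-BR23 breast items cover pain, swelling, sensitivity and skin problems. SAP 3.6.3 analyses them as mean score changes, not as serious events.
- Overall survival and the cause-of-death table (SAP 3.5.1, 3.4.1) pick up fatal events only.
- The exposure and treatment-violation outputs (SAP 3.4.4) describe treatment given.

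None counts non-fatal tumour complications.

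**Direction and scale**

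Let m be the arm A event rate (taken as fully recorded), r the arm B rate of tumour complications, and c the share of those that sites record as side effects.

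- Displayed difference, A minus B: m − c·r
- Difference with all events counted: m − r
- Bias: (m − c·r) − (m − r) = (1 − c)·r

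The bias is zero if c = 1 or r = 0. Otherwise it is positive, that is, against surgery. With the planned 127 patients per arm, one missed arm B patient adds 1/127 = 0.79 points. For scale, 127 × 0.018 = 2.3 and 127 × 0.057 = 7.2 arm A patients.

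The documents do not give r, so the values below are assumptions from 0% to 15%, with c = 0 as the worst case:

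| Assumed r | Arm B patients | m − r at m = 1.8% | m − r at m = 5.7% |
|---|---|---|---|
| 0% | 0 | +1.8 | +5.7 |
| 2% | 2.5 | −0.2 | +3.7 |
| 5% | 6.4 | −3.2 | +0.7 |
| 10% | 12.7 | −8.2 | −4.3 |
| 15% | 19.1 | −13.2 | −9.3 |

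In every row the table as displayed would show +1.8 or +5.7 points. These are not estimates. The 1.8% to 5.7% is general 30-day morbidity, which includes cardiac, embolic and renal events, and it is set against an arm B rate with no time limit.

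**The case against.** The strongest reply is that the documents show an undefined term and not a bias. SAP 3.7 says side effects without limiting them to effects of treatment, and nothing excludes tumour-related events. Both arms receive systemic therapy, and complications of on-demand surgery can count in arm B, so the table is not confined to the cost of the planned operation. Fatal sepsis enters overall survival, and on-demand therapy is listed by arm. The analysis is descriptive, with no test and no decision rule. All of this stands, and it makes the bias conditional.

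Three stronger readings are tempting and are not supported:

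- A reader might infer that bleeding, infected ulceration and sepsis in arm B are themselves classed as protocol deviations. They are not. The deviation is the local therapy, as the examples in SAP 3.4.2 show. The two records can coexist: a bleed in Table 16 and the resulting surgery in Table 17.
- A reader might infer that the comparison is already tilted against surgery. That depends on how sites record events, which the documents do not settle.
- A reader might infer from the illustration that the sign would reverse. That rests wholly on an assumed arm B rate and on an arm A figure that is not specific to local events. It also depends on the endpoint. The Protocol gives a 6% risk of a second operation for positive margins when frozen sections are used. If re-operations counted, the arm A rate would lie between 6% (complete overlap) and 5.7% + 6% = 11.7% (none). At r = 5% the difference would be +1.0 to +6.7 points, and at 10% it would be −4.0 to +1.7.

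The reply does not close the gap between measure and objective. The only planned measure, read in its ordinary sense, omits the harm the Protocol itself foresees in arm B, and no other output counts it when it is not fatal.

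**Conclusion.** The point holds in conditional form. A comparative safety objective rests on a treatment-linked count with no attribution rule, so local harm from the untreated primary may go uncounted in arm B while local harm from surgery is counted in arm A. If that happens, the bias is against surgery by 0.79 points per missed patient, taking 127 patients per arm and full recording in arm A. The total size, and whether the sign could change, cannot be stated from these documents. This is more than a missing definition, because the stated measure does not match the stated objective. It should be changed. It does not touch the primary analysis.

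**What to change.** - In SAP 3.7 and Table 16, add the number of patients with a serious local event of the breast, chest wall or axilla: bleeding, infection or sepsis, or ulceration. Count by randomised arm, whether the operation, the tumour or on-demand therapy was the cause, and over the same period in both arms. Give the between-arm difference with a 95% CI.
- Report re-operations and on-demand local procedures separately, with the reason where recorded. Inside the endpoint they would bring in re-excisions for margins in arm A and would treat arm B's own on-demand strategy as a harm.
- State that an entry in Table 17 does not remove the underlying event from the harm count.
- Reconcile the arm B wording of SAP 2.2.3, which appears to give both arms local therapy, with SAP section 2, which describes arm B as having none except on demand.

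The cost is SAP wording, one extra table and a review of the deviation and side-effect listings. Source checks may be needed, because the documents do not confirm that reasons for on-demand therapy are recorded. Conservatively managed events may still be under-captured, and the report should say so.
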